### **A. Objective**

Roche Cobas Liat Flu/RSV POC Assay and procalcitonin testing as part of a stewardship intervention optimizes antiviral treatment and reduces antibiotic treatment for ED patients (under 50 years of age) with suspected influenza or RSV v. standard care using a prospective, patient-randomized design. In addition to the primary outcome, we will evaluate secondary outcomes including aggregate physician adherence to CDC guidelines for the treatment of influenza, antibiotic duration, hospital admission, and emergency department (ED) return visits within 30 days for patients diagnosed with influenza and RSV. Additional secondary outcomes would include time to resolution of symptoms, return to school/work, and subsequent healthcare utilization (e.g. doctor visits) obtained through patient self-report.

Hypothesis: The rapid waived POC assay and procalcitonin, as part of a stewardship intervention will lead to reduced antibiotic treatment by 20 percentage points compared to the control group for antibiotic non-responsive conditions including ILI and nonspecific URI and will increase appropriate antiviral treatment of patients with influenza at high risk recommended to receive treatment by 20 percentage points.

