### **C. Study Population**

**Inclusion criteria:** Patients <50 who are evaluated by the clinician for suspected influenza, including symptoms of ILI (fever >38°C and cough or sore throat) or non-specific URI for whom the clinician suspects RSV or influenza or lower respiratory infection (with or without ordering a chest xray).

**Exclusion criteria:** Patients who are pregnant, prisoners, or are unable to give informed consent in English or Spanish. Patients with influenza-like illness and upper respiratory symptoms for whom the provider is unwilling to wait for procalcitonin results.

**Sample size:** We plan to enroll 100 patients in each arm over a 12 month period (influenza season), which will have 80% power to detect a true 20 percentage point reduction in antibiotic use and 20 percentage point increase in adherence to guideline recommendations for antiviral treatment.

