#### **E. Study Endpoints**

[figure not shown]
The primary study endpoint is the determination of whether use of the Roche Liat Flu/RSV Assay and procalcitonin testing, as part of a stewardship intervention optimizes antiviral treatment and reduces antibiotic treatment for ED patients with suspected influenza. The secondary study endpoints are aggregate physician adherence to CDC guidelines for the treatment of influenza, antibiotic duration, hospital admission, ED return visits within 30 days for patients diagnosed with influenza and RSV, time to resolution of symptoms, return to school/work, and subsequent healthcare utilization (e.g. doctor visits) obtained through patient self-report.

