#### **P. Statistical Analysis**

We will use standard descriptive statistics to summarize patient characteristics at randomization; mean and standard deviation (SD) for continuous variables and frequency and proportion for categorical variables. We will indicate the count of missing data for each variable. For the comparison of the primary outcomes, we will use frequency and proportions by arm, and compute a point estimate for the difference along with 95% confidence interval (CI) and p-value. We will stratify analysis based on flu status. For primary analyses (unstratified), we will use a Chi-square test (and Fisher exact test), and for stratified analyses, we used Mantel-Haenszel method. Secondary outcomes will be performed similarly. Statisticians and other investigators will remain blinded to treatment identity (e.g., data analyses with A/B coding). For all analyses, we will use SAS 9.4 (SAS Institute, Cary, NC).

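### The sample size is built on antiviral guideline adherence, which the endpoint sections rank as secondary, and no section names the antiviral primary outcome or its denominator

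*Combined protocol and SAP*

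**What the plan says.** The combined protocol and SAP describes the antiviral outcome in four places.

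- **Section C, sample size.** The design of 100 patients per arm is one "which will have 80% power to detect a true 20 percentage point reduction in antibiotic use" and a "20 percentage point increase in adherence to guideline recommendations for antiviral treatment". These are the only two outcomes given a power claim. No denominator is stated for adherence.
- **Section A, objective.** Adherence is secondary: "In addition to the primary outcome, we will evaluate secondary outcomes including aggregate physician adherence to CDC guidelines for the treatment of influenza". The hypothesis in the same section is about another quantity, namely that the intervention "will increase appropriate antiviral treatment of patients with influenza at high risk recommended to receive treatment by 20 percentage points".
- **Section E, endpoints.** The primary is whether the intervention, "as part of a stewardship intervention optimizes antiviral treatment and reduces antibiotic treatment for ED patients with suspected influenza". Adherence again comes under the secondary endpoints: "The secondary study endpoints are aggregate physician adherence to CDC guidelines for the treatment of influenza, antibiotic duration, hospital admission".
- **Section P, analysis.** "For the comparison of the primary outcomes, we will use frequency and proportions by arm". The plural is used, but the outcomes are not named. Secondary outcomes get the same analysis, and the section gives no significance level, order of testing or multiplicity rule.

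**The concern.** A reader cannot tell from the plan which antiviral comparison decides the antiviral half of the claim. Optimising treatment is an aim; it is not something that can be counted per patient. Two measures could fill the gap: adherence, which section C sizes, and treatment of high-risk patients with influenza, which section A hypothesises.

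These are different variables. If adherence is scored over everyone, it improves when unneeded antivirals are withheld. The high-risk measure does not change in that case, and it uses only a subset of the patients.

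Two things are at stake. If the choice is left until the data are seen, the antiviral claim does not have the error rate that a single test would have. And the stated 80% power belongs to one of the measures and may not belong to the other.

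**Working it through.** **Inputs from the documents.** 100 per arm, 80% power and a 20-point difference (section C); chi-square test with a 95% confidence interval (section P). The background in section B says that fewer than 40% of patients recommended for treatment receive it in the ED, but this is not named as a design input.

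**Assumptions.** Two-sided 5% level (not stated; the 95% interval is the only hint); 1:1 comparison without dropout; rates of 40% v 60%, which is the least favourable pair for a 20-point difference; 20 to 50 high-risk influenza patients per arm (the share is not given).

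**Formula.** With p̄ the mean of the two rates,

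power = Φ{[√n·|p₁−p₂| − 1.96·√(2p̄(1−p̄))] / √[p₁(1−p₁)+p₂(1−p₂)]}.

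At 40% v 60%, √(2p̄(1−p̄)) = √0.50 = 0.7071, so 1.96 × 0.7071 = 1.386; and √(0.24+0.24) = 0.6928.

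**Step 1: the plan's own figure.** With n = 100: (2.000 − 1.386)/0.6928 = 0.886, power 81.2%. The size for 80% is 97 per arm. Other pairs do better: 82.8% at 30% v 50% and 87.6% at 20% v 40%. Fisher's exact test gives 78.7% at 40% v 60%. The stated 80% is therefore sound for an outcome measured in all 100 per arm.

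**Step 2: the hypothesised measure.** The same formula on the subset:

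| High-risk influenza patients per arm (assumed) | Numerator | Power |
|---|---|---|
| 20 | 0.894 − 1.386 = −0.491 | 23.9% |
| 30 | 1.095 − 1.386 = −0.290 | 33.8% |
| 50 | 1.414 − 1.386 = 0.028 | 51.6% |

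**Step 3: error rate if either measure may carry the claim.** Two tests at 5%:

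- independent: 1 − 0.95² = 9.75%
- correlation 0.5 (bivariate normal): 9.1%
- correlation 0.8: 7.8%

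**Step 4: does adherence in all randomised patients keep the 80%?** Only if that overall proportion truly moves by 20 points. Suppose that high-risk influenza patients go from 40% to 60% treated, that treatment among the others falls from 15% to 5%, and that adherence means treated if recommended and untreated otherwise (all assumed).

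- 15% share: control 0.15×0.40 + 0.85×0.85 = 78.25%; intervention 0.15×0.60 + 0.85×0.95 = 89.75%; difference 11.5 points.
- 30% share: control 0.30×0.40 + 0.70×0.85 = 71.5%; intervention 0.30×0.60 + 0.70×0.95 = 84.5%; difference 13 points.

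Power at 100 per arm is about 60% in both cases, and 80% would need about 160 per arm.

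**The case against.** The best defence is that section C never calls adherence primary. Both places that rank endpoints call it secondary, and powering an outcome does not by itself change its rank. The sample-size sentence could also be shorthand for the hypothesis in section A: both say 20 points, and both concern recommended treatment. The first part stands: the primary rank of adherence is an inference. But it does not close the gap. If adherence is secondary, the antiviral primary has no sample-size basis. If the sentence is shorthand, the 80% applies only if nearly every enrolled patient is at high risk and has influenza.

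Two mitigations deserve weight. Section F calls the trial a pilot, and section P keeps statisticians and investigators blinded through A/B coding. They soften the consequence. They do not name the outcome, and the plan still states power, a directional hypothesis and p-values.

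Three stronger readings are tempting and are not supported:

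- *Raw antiviral use is a third candidate*, which would put the false-positive rate at 1 − 0.95³ = 14.3% if independent. It appears only in a list of data to be collected and compared, beside items such as disposition and isolation, with no hypothesis or effect size.
- *The two measures would often give opposite verdicts.* Any such frequency rests on treatment rates that the documents do not give, and would largely reflect the unequal power shown in steps 2 and 4.
- *A failed primary will be rescued by the other measure.* The plan does not prevent this, but nothing in it shows such an intention.

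**Conclusion.** The point holds as a conflict in the current text about endpoint rank and definition. The sized antiviral outcome is ranked secondary, the hypothesised one is not the one sized, and the analysis section names neither. The power calculation is not itself wrong: it reproduces at 81.2% when all 100 per arm count. It does not carry over to the high-risk influenza measure, where power is about 24% to 52% for 20 to 50 such patients per arm. With two supportable candidates and no rule between them, the false-positive rate for the antiviral claim is about 7.8% to 9.8%, if either may carry it.

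These sizes depend on the assumed two-sided 5% level, the 40% v 60% rates, the correlation range and the assumed number of high-risk influenza patients. The mismatch between sections depends on none of them. Whether success on antibiotics, antivirals or both is required is a separate question.

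**What to change.** Before the data are seen, the sponsor should:

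1. Name one antiviral primary outcome, with its denominator and a written scoring rule applied identically in both arms.
2. Give it the same rank in sections A, C, E and P, put it in place of the general wording about optimising treatment in section E, and make the other antiviral measure secondary.
3. List the primary outcomes by name in section P.
4. Restate the power in section C for the outcome chosen. For the high-risk influenza measure, base it on the expected number of such patients. For adherence in all randomised patients, keep 80% only for a true 20-point difference in that overall proportion; step 4 shows how the true difference could be smaller.

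Either measure is a legitimate choice, and the documents do not settle it, so the decision is the sponsor's.

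Cost: wording in four sections and one power statement, with no extra patients required. The downside is that the sponsor gives up the choice of headline antiviral measure, and the stated power may become less favourable.

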#### **F. Research Design and Methods**

This will be a prospective, patient-oriented, pilot randomized clinical trial to evaluate (in aggregate) both the use of the Flu/RSV Assay, procalcitonin, and the use of pharmacist-led education for providers in the interpretation of these test results. Children and adults <50 years of age who present to the pediatric ED of the UC Davis Medical Center with influenza-like illness (ILI), upper or lower respiratory infection (URI) will be eligible to participate.

Consented patients in the pediatric ED will be randomized into two arms: The intervention arm will receive procalcitonin with a patient specific stewardship intervention during the ED visit. The intervention will be pharmacist-led and include direct delivery to clinicians of information about interpreting test results and recommendations for antiviral-treatment for high-risk patients, and infection control precautions for patients being hospitalized with a positive RSV or influenza test and avoidance of antibiotics where not indicated. Clinician adherence to treatment guidelines with and without the educational intervention will be compared. Patients randomized to this arm will also have 1 ml of blood drawn for procalcitonin (PCT) analysis to identify bacterial infections. This sample will be taken at the time of a blood draw for standard clinical labs, or from an IV if one is in place. If no blood draw is ordered for standard of care and/or no IV is placed, patients will be given the option to consent to an extra needle stick for the purpose of research if both the clinician and patient agree to wait for the test result. Interpretation of the procalcitonin where obtained will be included in the intervention by the ED pharmacist. We will use the following protocol to guide clinicians in recommendations for antibiotic therapy. Procalcitonin will be an adjunct to guiding decision making for antibiotic use and will provide added value for both patients diagnosed with RSV and flu, as well as promote reduced antibiotic use for patients who do not have diagnosed flu or RSV and help guide appropriate treatment for those patients suspected of having LRTI. We will use a conservative protocol in both infants and older children similar to the figure attached but with a cutoff of 0.5 for recommendation of initiation of therapy in patients suspected of having LRTI.

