## LRTI Initial Antibiotic Use Algorithm

The second arm will be standard care.

Physicians and patients will not be blinded to test type. Tests will be performed on a real-time basis in the ED. All results will be delivered via standard of care through the EMR.

For each of these groups, data of the frequency and duration of antibiotic administration, antiviral use, adherence to evidence based guidelines for treatment of influenza, disposition, concomitant diagnoses, isolation, hospitalizations, and unscheduled return visits or readmissions within a 30 day period will be collected and compared. In addition, we will compare procalcitonin levels for patients diagnosed with RSV or influenza by the Roche LIAT in the test arm compared to those found to have evidence of bacterial infection based on chest xray, blood culture, and other ancillary tests. Where not recommended, reason for antibiotic use will be documented by the pharmacist and abstracted from chart review.

Research coordinators will contact patients and/or parents at 1 and 4 weeks after enrollment for self-reported secondary outcomes including symptom resolution, return to school/work, and follow up healthcare visits, medication adherence (to antibiotics and/or antivirals), and adverse events.

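### Does asking about willingness to wait for procalcitonin after randomisation let patients drop out of one arm only?

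*Combined protocol and SAP*

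**What the plan says.** **Entry.** Section C, under the exclusion criteria, lists "Patients with influenza-like illness and upper respiratory symptoms for whom the provider is unwilling to wait for procalcitonin results". It gives no time point and does not say who records the answer.

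**Allocation and the PCT draw.** Section F states: "Consented patients in the pediatric ED will be randomized into two arms". For the intervention arm it continues: "Patients randomized to this arm will also have 1 ml of blood drawn for procalcitonin (PCT) analysis". The sample comes from a routine draw or an existing IV where there is one. Otherwise the patient may consent to an extra needle stick "if both the clinician and patient agree to wait for the test result". The section then adds: "Interpretation of the procalcitonin where obtained will be included in the intervention by the ED pharmacist".

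**Control arm.** Under the algorithm heading that follows Section F: "The second arm will be standard care". The same part of the protocol says that antibiotic use, antiviral use and the other outcomes are collected and compared for each group.

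**Analysis.** For the primary outcomes, Section P says "we will use frequency and proportions by arm", with a chi-square (and Fisher exact) test. It names no analysis population. Section H lets the treating physician withdraw a patient on grounds of prudence and does not mention PCT.

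**The concern.** Agreement to wait for PCT appears twice: as an eligibility matter in Section C and as a condition in Section F for patients already allocated to the intervention. Controls have no study PCT and never reach the second question. The trial is open label, so a clinician answering it knows the arm. If staff read a refusal at that point as meeting the Section C exclusion, patients would leave one arm only.

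That would be serious. Patients whose clinician will not wait may differ in their chance of receiving an antibiotic, and analysis could not reliably repair the loss. If they stay in the trial untested, the worry becomes dilution: the antibiotic contrast could fall below the 20 points on which the stated 80% power rests. With no intention-to-treat sentence in Section P, neither outcome is ruled out in so many words.

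**Working it through.** **1. The plan's own figure.** Inputs from Section C: 100 per arm, 80% power, 20-point difference. Assumptions, because the documents give neither: two-sided 5% (in line with the 95% interval in Section P) and the base rate. The least favourable case is 60% versus 40%, with pooled rate 0.5:

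n = [1.960·√(2·0.5·0.5) + 0.842·√(0.6·0.4 + 0.4·0.6)]² / 0.20² = 96.9, so 97 per arm.

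Power at 100 per arm is 81.2% by this formula and 82.6% by exact enumeration of the uncorrected chi-square test. The stated size holds.

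**2. The two clauses compared.**

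| | Section C | Section F |
|---|---|---|
| Function | Decides who enters | Decides whether an extra needle stick is offered |
| Whose agreement | Provider | Clinician and patient |
| Patients covered | Influenza-like illness and upper respiratory symptoms | Intervention patients with no routine draw and/or IV |
| If not met | Not enrolled | No extra stick, so possibly no PCT result |

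Both can be followed as written. A provider may be willing at screening and the patient may later decline the stick. That patient has no PCT result but is still in the trial. The words "where obtained" within "Interpretation of the procalcitonin where obtained will be included in the intervention by the ED pharmacist" only make sense if such patients exist in the intervention arm.

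**3. What one-arm exclusion would do, if it happened.** Assume no true effect, an overall antibiotic rate of 50%, and 20% of the intervention arm removed. If those removed have a 70% rate, the rest have (0.50 − 0.20·0.70)/0.80 = 45%, a spurious 5-point reduction. If they have a 30% rate, the rest have (0.50 − 0.20·0.30)/0.80 = 55%, a spurious 5-point increase. These rates are assumptions. The documents give neither size nor direction, and they plan no such removal.

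**4. Dilution, if untested patients stay in.** Let u be the untested share and k the fraction of the effect they keep through the pharmacist's advice. Difference = 20·[(1 − u) + u·k] points. Exact power at 100 per arm is shown as a range from k = 0 to k = 0.5:

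| Control rate (assumed) | u = 0 | u = 10% | u = 20% | u = 30% |
|---|---|---|---|---|
| 60% | 82.6% | 74.2–78.6% | 64.1–74.2% | 53.0–69.3% |
| 40% | 88.0% | 79.6–84.1% | 68.7–79.6% | 56.3–74.4% |
| 30% | 95.6% | 89–93% | 79–89% | 66–85% |
| 25% | 98.9% | 95–98% | 87–95% | 75–92% |

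With k = 1 nothing is lost at any u.

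**5. What the 20 points refer to.** The table presumes that 20 points is the effect in tested patients. Section A attaches it to the assay and PCT as parts of a stewardship intervention, compared with control. Section F says the components are evaluated in aggregate and expects some patients to have no PCT. Read that way, 20 points is the arm-level effect of the strategy as delivered, incomplete testing included. Then u is already inside the 20 points and the relevant power is the u = 0 column.

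**The case for a change.** The strongest counter-argument is that convention is not a rule. Had willingness been settled for every candidate before randomisation, Section F would hardly need to ask the clinician again, at least for the patients Section C covers. Section P has no analyse-as-allocated sentence, Section H does not deal with a refusal to wait, and a coordinator facing an unwilling clinician after allocation has no written instruction. Calling the trial a pilot is no answer, because the plan claims 80% power and will report p-values and confidence intervals. The remedy would cost two questions and two sentences.

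Part of this stands. The time point is not written down and the analysis population is not named. The power figures in the first two rows of the table are also correct on their premise. What does not follow is that the plan, carried out as written, goes wrong. The repeated question has its own purpose, since an extra needle stick for research needs the patient's agreement and is pointless if nobody will wait for the result. That controls do not face it simply reflects that they have no study PCT. The power loss depends on a premise the documents do not adopt, and on control rates and untested shares they do not give.

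**Conclusion.** No change follows. The exclusion belongs at entry, the later clause governs only an optional blood draw, intervention patients without PCT are foreseen, and outcomes are collected and compared by group. An analyst following this text would keep every randomised patient in the allocated arm, which is the sound analysis. Writing down the time point and an analyse-as-allocated sentence would record what the text already implies.

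On size, no stated figure is shown to be wrong: 100 per arm gives at least 80% power for a 20-point arm-level difference even in the least favourable case. If the 20 points is instead assigned to tested patients only, 20% untested would leave power between 64.1% and 95%, depending on the control rate (60% down to 25%) and on how much pharmacist advice achieves without PCT. The documents fix none of these quantities.

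The conclusion rests on two readings: that an exclusion criterion is applied before randomisation, and that the 20-point effect belongs to the package. If patients were in fact removed after allocation because PCT was not obtained, that would depart from the plan and the bias concern would become real.
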